#### **Inclusion criteria:**

Women between ages 21-42 years seeking IVF. Participants must be willing to undergo acupuncture and have no contraindications to needle insertion.

#### **Exclusion criteria:**

Women currently using alternative therapies such as acupressure, herbal supplements and meditation techniques will be excluded. Women with generalized psoriasis, neuropathy or coagulopathies posing increased risk due to needle insertion will also be excluded. Women must also agree not to take NSAIDs during their IVF treatment. Therefore women whom do not agree to avoid NSAIDs will be excluded from the study.

After fulfilling all requirements for inclusion in the study, patients will be randomized to the treatment group or the control group based upon random numbers generated before beginning the trial. The random numbers will be placed in consecutively numbered sealed envelopes.

[figure not shown]
## *Intervention*

### *Acupuncture Protocol for treatment group*

An acupuncture treatment protocol will be followed using a Delphi consensus process developed specifically for patients undergoing IVF (Smith CA , Grant S , Lyttleton J , Cochrane S . 2012) . This Delphi consensus protocol is developed by 17 international and national acupuncturists working in the fertility area. The points and timing were carefully chosen based on acupuncturists' experiences as well as research reviews. For instance, applying the third session of acupuncture on the day of transfer is supported by six systematic reviews (Kang, 2011).

Three semi-standardized sessions of manual acupuncture treatment will be administered during an IVF cycle including ET. Each session will run about 30~40 minutes at either the Family Medicine Clinic or Center for Fertility and Reproductive Surgery. The expense of all three sessions will be reimbursed by the project, NOT billed to the participant. The first treatment will be administered between days 6 through 8 of the stimulated IVF cycle, and will include core points ST29, CV4, CV6, SP6, SP10, plus up to 5 individualized additional points based on TCM pattern differentiation. The second treatment, prior to transfer on the day of embryo transfer, will use points SP8, SP10, LR3, ST29, CV4 and one selected from HT7/PC6/YinTang (depending on presentation of women). The third treatment to be done post-embryo transfer (any time following ET but before the pregnancy test) will use points GV20, KD3, ST36, SP6, PC6). This visit will occur within a windowed timeframe (within 48 hours post transfer, if possible, which includes anytime post-transfer on embryo transfer day) acknowledging the participant's ability to return during that timeframe. Main points are shown in Figure 1 and all points will be located based on WHO Standard Acupuncture Point Locations 2008 version. Up to 20 needles per session may be used. Disposable stainless-steel acupuncture needles (0.16×15 mm, 0.18 ×30mm and 0.20X40mm, DBC Spring Ten, Korea) will be used. Needles will be inserted manually to a depth varying from  $10\pm5$ mm to  $25\pm5$  mm at the acupoints depending on the location and patient's physical figure. Needle retention time will be 25 minutes.

Figure1. Selected main acupoints for IVF protocol

Auricular acupuncture using points Shenmen and Zigong only will be used on the day of ET. Needling sensation, *De qi*, is a composite of unique sensations interpreted as the flow of Qi or ‘the arrival of vital energy’. *De qi* will be maintained with additional stimulation during the initial treatment on day 6–8, and during the pre-embryo treatment.

#### *Control Group*

The participants in the comparison group will continue their current usual IVF care at the Center for Fertility and Reproductive Surgery. Participants in the control group will also be asked to attend three study visits. The first visit will take place between days 6-8 of the IVF cycle. The second visit will take place on the day of embryo transfer, prior to transfer. The third visit will take place post-embryo transfer but before the pregnancy test. This visit will occur within a windowed timeframe (48 hours post transfer, which includes anytime post-transfer on embryo transfer day) acknowledging the participant’s ability to return during that timeframe. At the beginning and end of each study visit, participants will provide a urine sample.

Study participants in this group will receive vouchers for 3 future acupuncture sessions, provided at no cost to them. These vouchers will be provided on the day of the participant’s embryo transfer, or mailed to them after embryo transfer, and may be used beginning 1 year from the date of the embryo transfer. In the event that embryo growth does not progress or implantation is cancelled for any reason, the subject’s participation in this study will end. For those subjects vouchers will be mailed to them after study visit 1 and will be valid beginning one year from study visit 1. The vouchers will then be valid for 1 year. (i.e., Control group embryo transfer on 6-1-15. Patient receives 3 acupuncture vouchers that are valid 6-1-16 through 6-1-17). The delayed use of the acupuncture vouchers is intended to avoid use of the acupuncture sessions during pregnancy in the control group which could potentially affect outcome data comparisons between the two groups. For the same reason, subjects will be asked to commit to abstaining from acupuncture for the same period of 1 year post-embryo transfer, should they be randomized to the control arm. In event of error, vouchers may be replaced by mailing new ones to the subject.

#### *Determination of Stable Metabolites of Prostacyclin and Thromboxane in the Urine*

Urine samples will be collected from all study participants prior to and after each acupuncture session for the treatment group, and before and after each study visit for the control group. Stable metabolites of thromboxane and prostacyclin, 2, 3-dinor-TXB2 and 2, 3-dinor-6-keto-PGF1α, respectively will be determined on a later date. Specifically, a mid-stream urine sample will be collected in a sterile wide-mouth container. A 10mL aliquot will be centrifuged (300x g) for 10 min and the supernatant kept at -20C until assay. Stable metabolites of prostacyclin and thromboxane will be determined using ELISA kits according to the manufacturer’s protocol: TXB2 ELISA kit (Enzo Life Sciences, Inc., <http://www.biocompare.com/9956-Assay-Kit/1371009-TXBsub2sub-ELISA-kit/>), Urinary prostacyclin ELISA kit (Enzo Life Sciences, Inc., <http://www.enzolifesciences.com/ADI-900-025/urinary-prostacyclin-elisa-kit/>). The specification of the kit shows that both kits have fairly high sensitivity. The lowest detection limits for TXB2 and prostacyclin metabolites are 10.54pg/mL and 6.58pg/mL, respectively. We plan to perform preliminary tests to determine the appropriate dilution of the samples before assay. In case the concentrations are below the detection limits, samples will be concentrated using a Centricon® Filter Concentrator (Millipore Co.). In case the above method cannot increase the concentration to within detectable ranges, GC/MS methodology will be used– we will consult collaborators ([name], University of Houston) who determine prostacyclin and thromboxane metabolites using GC/MS on a routine basis.

#### *Assessment of Self-Perceived Stress in Treatment and Control Group*

To determine whether acupuncture contributes to stress reduction, study participants in the treatment group will complete the Perceived Stress Scale (Cohen, 1983 see Addendum) to assess self-perceived stress cycle days 6 through 8 of ovarian stimulation, on the day of embryo transfer, pre-embryo transfer and post-embryo transfer, but before the

pregnancy test, within 48 hours of transfer. Participants in this group will complete this scale before and after their acupuncture treatment.

Study participants in the control group will complete the same Perceived Stress Scale questionnaire once during days 6 through 8 of ovarian stimulation, on the day of embryo transfer, pre-embryo transfer and post-embryo transfer, but prior to the pregnancy test, within 48 hours of transfer.. In the event that the embryo transfer must be postponed for clinical reasons, the post-treatment questionnaire will be performed 3 to 7 days after the oocyte retrieval.

#### *Study Data*

The following data will be recorded for this study:

- Urine test collection date/time and results
- Acupuncture (control group wait) date/start/stop times
- Perceived Stress Scale data
- Age and race
- Pregnancy test results (+ pregnancy test (y/n), + clinical pregnancy (y/n))
- Pregnancy outcome (live birth (y/n))

#### *Potential Problems and Alternative Approaches*

#### *Recruitment*

Patients at the Center for Fertility and Reproductive Surgery will be screened for eligibility by [name] and [name] and, if eligible invited to take part in this study. We do not anticipate any problem recruiting enough individuals to participate in the investigators' study. The Texas Tech University Health Sciences Center, Center for Fertility & Reproductive Surgery currently performs approximately 70 IVF cycles per year. Even if 50% of patients participate in the study we have 70 patients in a 2 year period.

#### *Poor Response to Egg Retrieval*

Subjects whom are enrolled in the study who have a poor response to initial medication stimulation (identified early in the treatment cycle, warranting cancelling and new medication plan) can continue to be in the study if they plan on having retrieval at a later date. The subjects would be re-consented if changes were made to the ICF since the time they were last consented to be in the study. There would be no new randomization done. The subject would continue with their last randomization number and their previous ID. The subject will proceed in the study and continue with the study procedure visits #1- 3 when they return for future IVF.

#### *Enzyme immunoassay of metabolites of prostacyclin and thromboxane:*

In case the concentrations are below the detection limits, samples will be concentrated using a Centricon® Filter Concentrator (Millipore Co.). In case the above method cannot increase the concentration to within detectable ranges, GC/MS methodology will be used. We have collaborators ([name]., University of Houston) who determine prostacyclin and thromboxane metabolites using GC/MS on a routine basis.

#### *Psychological testing*

We do not anticipate any problem administering psychological testing. One of the investigators is an experienced clinician. She administered the proposed test many times in her career.

#### *Removal from study*

In the event that embryo growth does not progress or implantation is cancelled for any reason, the subject's participation in this study will end.

### Risks

Participation in this study will not change the standard risks related to in vitro fertilization. Those who are randomized to the experimental group will undergo acupuncture. Acupuncture is generally considered safe when done by a trained professional. Risks of acupuncture may include occasional dizziness, bleeding, bruising, and potential anxiety. However, women who undergo IVF will perform up to 80-100 subcutaneous and intramuscular injections on themselves by the time of receiving acupuncture. Comparing to the bigger gauge (thicker hollow needle) of the syringe needles, discomfort caused by acupuncture needle will be similar but at a much lower level. Possible loss of confidentiality is a risk for all study participants, and will be mitigated by de-identifying all study data.

### Benefits

Prior studies indicate a potential benefit of acupuncture on in vitro fertilization outcomes. However, the mechanism of the benefit is unclear. It is possible that taking part in this study will be of no benefit to the participant.

### Confidentiality

Each subject will be assigned a unique identification number at the time of enrollment, and all data will be de-identified and labeled with the subjects' ID number. All de-identified data will be stored securely on encrypted devices accessible only to study investigators in accordance with TTUHSC policies.

### *Projected Timeline*

Historically, patients seeking infertility treatment with IVF are open-minded to alternative therapy to enhance success. The TTUHSC Center for Fertility and Reproductive Surgery currently performs 70 IVF cycles per year. With a projected recruitment of 50% of women undergoing IVF, we anticipate reaching the investigators' goal of 70 subjects in a 2-year period.

### *Significance or Innovation of Expected Research Outcome*

Acupuncture shows promise in enhancing success rates in women undergoing IVF. However, without an established mechanism of action, it is difficult to encourage patients to accept the treatment. Furthermore, understanding the mechanism of acupuncture's positive effect (i.e., increased vasoactive biomarkers and/or decreased perceived stress) may lead to the development of other treatment modalities to help infertile women. Finally, the general population may be more likely to accept this low-risk, affordable alternative treatment modality if we can provide a scientific explanation of the beneficial effects of acupuncture.

**Addendum:**

## **PERCEIVED STRESS SCALE by Sheldon Cohen**

The *Perceived Stress Scale* (PSS) is the most widely used psychological instrument for measuring the perception of stress. It is a measure of the degree to which situations in one's life are appraised as stressful. Items were designed to tap how unpredictable, uncontrollable, and overloaded respondents find their lives. The scale also includes a number of direct queries about current levels of experienced stress. The PSS was designed for use in community samples with at least a junior high school education. The items are easy to understand, and the response alternatives are simple to grasp. Moreover, the questions are of a general nature and hence are relatively free of content specific to any subpopulation group. The questions in the PSS ask about feelings and thoughts during the last month. In each case, respondents are asked how often they felt a certain way.

**Evidence for Validity:** Higher PSS scores were associated with (for example):

- failure to quit smoking
- failure among diabetics to control blood sugar levels
- greater vulnerability to stressful life-event-elicited depressive symptoms
- more colds

**Health status relationship to PSS:** Cohen et al. (1988) show correlations with PSS and: Stress Measures, Self-Reported Health and Health Services Measures, Health Behavior Measures, Smoking Status, Help Seeking Behavior.

**Temporal Nature:** Because levels of appraised stress should be influenced by daily hassles, major events, and changes in coping resources, predictive validity of the PSS is expected to fall off rapidly after four to eight weeks.

**Scoring:** PSS scores are obtained by reversing responses (e.g., 0 = 4, 1 = 3, 2 = 2, 3 = 1 & 4 = 0) to the four positively stated items (items 4, 5, 7, & 8) and then summing across all scale items. A short 4 item scale can be made from questions 2, 4, 5 and 10 of the PSS 10 item scale.

**Norm Groups:** L. Harris Poll gathered information on 2,387 respondents in the U.S.  
**Norm Table for the PSS 10 item inventory**

Category	N	Mean	S.D.
Gender			
Male	926	12.1	5.9
Female	1406	13.7	6.6
Age			
18-29	645	14.2	6.2
30-44	750	13.0	6.2
45-54	285	12.6	6.1
55-64	282	11.9	6.9
65 & older	296	12.0	6.3
Race			
white	1924	12.8	6.2
Hispanic	98	14.0	6.9
black	176	14.7	7.2
other minority	50	14.1	5.0

## Perceived Stress Scale

The questions in this scale ask you about your feelings and thoughts **during the last month**. In each case, you will be asked to indicate by circling *how often* you felt or thought a certain way.

Name \_\_\_\_\_ Date \_\_\_\_\_

Age \_\_\_\_\_ Gender (Circle): **M** **F** Other \_\_\_\_\_

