## Project Abstract

Infertility affects 12% of couples in the United States. In vitro fertilization (IVF) is the most advanced treatment for infertility. Despite decades of improvements in hormonal drug therapy and laboratory techniques, IVF embryos continue to have low implantation potential (~30%/embryo). Therefore, it is not uncommon to transfer multiple embryos to the uterus in order to enhance success. As a result, approximately 30% of IVF pregnancies result in multiple gestation, which lead to higher morbidity and mortality of the mothers and infants. The best method to reduce multiple birth and associated morbidity and mortality is to transfer a single embryo with enhanced implantation potential. A recent meta-analysis of acupuncture for IVF showed it may augment IVF success by ~10%, although the underlying mechanism remains unclear. We hypothesize that acupuncture enhances IVF success by enhancing the perfusion of pelvic organs including the ovaries and the uterus. Since undergoing IVF treatment is a stressful process to most patients, we further hypothesize that acupuncture stabilizes the mind-body interaction by optimizing the psychological well-being of patients receiving IVF treatment.

Experimental Approach: (1) Participants: Women (ages 21 to 42) who seek IVF treatment at the Center for Fertility & Reproductive Surgery will be eligible for the study. Seventy women will be recruited and randomly assigned to either the intervention (acupuncture plus standard care) or the comparison (standard care alone) group. (2) Intervention: Participants in the intervention group will receive 3 acupuncture sessions during the project with the first treatment between day 6–8 of the stimulated IVF cycle, second treatment on the day of embryo transfer and the third treatment post-transfer, within 48 hours. Participants in the comparison group will receive no intervention but will receive standard care. (3) Measures: The primary outcome measures include prostacyclin and thromboxane vasoactive biomarkers. Secondary outcome measures include perceived stress levels. (4) Procedure: Upon IRB approval, an informed consent will be provided to all participants. Pre- and post- acupuncture urinary metabolites of prostacyclin and thromboxane will be assessed. A standardized Perceived Stress Scale will be administered before each acupuncture session for the study group, and before a 30-40-minute waiting period for the control group.

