### **Specific Aims:**

- (1) To measure the effects of acupuncture on key vasoactive urine molecules, i.e. prostacyclin and thromboxane, before and after acupuncture, and
- (2) to assess the impacts of acupuncture on the psychological well-being of women undergoing IVF treatment.

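### The PSS asks about the last month, so its change across one 30-40 minute session cannot be read as an acupuncture effect, and the between-arm effect at visits 2 and 3 is diluted

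*Combined protocol and SAP*

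**What the plan says.** Specific Aims gives the second aim as "to assess the impacts of acupuncture on the psychological well-being of women undergoing IVF treatment". The PSS is the only psychological measure under Study Data.

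**Recall window.** The form states: "The questions in this scale ask you about your feelings and thoughts during the last month". The scale description in the Addendum agrees: "The questions in the PSS ask about feelings and thoughts during the last month". Each of the ten printed items opens with the same one-month reference.

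**Timing, acupuncture arm.** Assessment of Self-Perceived Stress places the PSS at stimulation days 6-8, on transfer day before transfer, and after transfer within 48 hours, and adds: "Participants in this group will complete this scale before and after their acupuncture treatment". On session length, the acupuncture protocol says: "Each session will run about 30~40 minutes".

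**Timing, control arm.** The same section says: "Study participants in the control group will complete the same Perceived Stress Scale questionnaire once during days 6 through 8 of ovarian stimulation", followed by the same transfer-day and post-transfer points. It describes no before/after pair.

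**Timing, abstract.** The Project Abstract says: "A standardized Perceived Stress Scale will be administered before each acupuncture session for the study group", and before a waiting period of 30-40 minutes for controls. It mentions no post-session form.

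The plan names no PSS contrast and no main PSS time point. The only test mentioned is the two-sample t-test in the Power analysis.

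**The concern.** A recall period has to match the interval over which change is measured. Two forms completed on either side of one session ask about practically the same month. A woman who follows the instructions has almost nothing new to report, so a shift is more likely to reflect her mood at that moment or what she expects of an unblinded treatment. With no after-form in the control arm, that shift cannot be set against a control change either.

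Across visits the problem is milder. A form at visit 2 or 3 may mix days before and after session 1, which pulls a real difference between arms towards zero. At stake are a treated-arm before/after change that may be reported as stress reduction, and a true effect that may be missed or underestimated. The plan intends to use these pilot data to size later studies, so an underestimate would carry forward.

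**Working it through.** **Inputs from the documents:** one-month recall (PSS form); sessions of 30-40 minutes (acupuncture protocol); visit 1 at stimulation days 6-8; visit 2 on transfer day; visit 3 within 48 hours of transfer *if possible*, and possibly on transfer day itself; last form 3-7 days after retrieval if transfer is postponed; 35 per group, d = 0.6, alpha 0.05, power 0.80 (Power analysis).

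**Assumptions:** a month is 30 days. The visit 1-to-transfer gap is not given; Research Design and Methods says only that the three visits fall in an 8-week cycle. I use 7-14 days as an illustration.

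**1. The plan's own figure.** Power is the chance that a noncentral t with 68 df and noncentrality d × √(n/2) exceeds the critical value. Here 0.6 × √17.5 = 2.51. One-sided (critical value 1.668) power is 0.80, as stated. Two-sided (1.995) it is 0.70. The stated figure therefore reproduces only one-sided; the plan does not state sidedness, so both are shown below.

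**2. Within a session.** 30 days = 30 × 1,440 = 43,200 minutes.
- 30 / 43,200 = 0.07%
- 40 / 43,200 = 0.09%

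The overlap of the two windows is 99.91-99.93%. At visit 1 both forms describe a month almost wholly before the first needling.

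**3. Between visits.** Share of the window after session 1 = days since session 1 / 30.
- Visit 2: 7/30 = 23% to 14/30 = 47%
- Visit 3: 7/30 = 23% (same day as transfer) to (14 + 2)/30 = 53% (two days later)
- More than half follows session 1 once the gap exceeds 15 days; all of it does from 30 days.

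A second set of assumed timings, with retrieval on stimulation day 10-16 and the last form 3-7 days later, gives 5-17 days since visit 1, or 17-57%.

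**4. What dilution could cost.** Suppose answers average evenly over the window and the effect is constant from session 1. Observed d = 0.6 × share:

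| Days since session 1 | Share | Observed d | Power, one-sided | Power, two-sided |
|---|---|---|---|---|
| 7 | 0.23 | 0.14 | 0.14 | 0.09 |
| 14 | 0.47 | 0.28 | 0.31 | 0.21 |
| 16 | 0.53 | 0.32 | 0.38 | 0.26 |
| 30 | 1.00 | 0.60 | 0.80 | 0.70 |

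Even averaging is a working model that the documents do not state. If women give more weight to recent days, the loss is smaller.

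I leave these results in d units because the Power analysis treats 6.2 as a variance (0.6 × √6.2 = 1.5 points), whereas the norm table lists 6.2 as an S.D. (0.6 × 6.2 = 3.7 points). That is a separate matter, and the shares above do not depend on it.

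**The case against.** The strongest reply is that the only comparison in the plan is between two independent samples. Both arms use the same wording, and randomisation balances the pre-treatment days, so the arms can still be compared fairly at visit 2 or 3. No within-session PSS contrast is specified, and the abstract does not mention an after-form. This stands: the between-arm comparison is diluted, not void. It does not excuse collecting an after-form that has no sound use.

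A second reply points to the scale description: "The scale also includes a number of direct queries about current levels of experienced stress". None of the ten printed items asks about the present, so this does not rescue the before/after pair. It is still fair to say that respondents may lean on recent feelings, which makes even averaging a pessimistic model.

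A third reply is that a long delay before transfer could put most or all of the window after session 1. That is possible, since the gap is unstated and the 48-hour limit is qualified. It is partly limited by the rule that, if transfer is postponed, the last form is completed 3-7 days after retrieval.

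Finally, the PSS is a secondary outcome in a pilot, and the primary biomarkers are unaffected. That bears on priority, not on whether the mismatch exists.

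**Conclusion.** The concern holds in two parts of different strength.

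**Firm:** with at least 99.9% overlap of recall windows, the within-session PSS change in the acupuncture arm is not interpretable as an acupuncture effect. This needs only a 30-day month and answers that follow the form. The abstract and the assessment section also disagree on whether an after-form exists, and must be reconciled.

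**Conditional:** at visits 2 and 3 the between-arm effect is diluted by an amount that depends on the unstated visit 1-to-transfer gap. With an assumed gap of 7-14 days, about 23-53% of the window follows session 1. The power figures also rest on even averaging over the window and a constant effect.

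A reader might infer that Aim 2 cannot be answered, or that most of every recall window predates acupuncture. The documents support neither. The randomised comparison remains valid with reduced sensitivity. The claim about *most* of the window is certain only at visit 1; for later visits it depends on the gap, and the illustrative range itself passes one half.

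**What to change.** 1. Give the PSS once per visit, before the session or wait, in both arms. Drop the post-session PSS and any before/after PSS comparison. Bring the Project Abstract and the assessment section into agreement.
2. In place of the after-form, add one 0-10 item, *how stressed do you feel right now*, at the start and end of every visit in both arms. Label it exploratory: the trial is open-label without sham, so expectation can move this rating too.
3. Name the Aim 2 comparison: visit 3 PSS between arms, adjusted for the visit 1 pre-session PSS. Describe it as month-averaged perceived stress that includes pre-treatment days. Report the days from visit 1 to each later form so that the dilution can be judged.
4. If the recall wording is shortened at visits 2 and 3, anchor it to *since your first study visit*. Anchoring to the last visit would be unsound, because visit 3 may fall on transfer day and the window would then cover only hours.

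**Cost:** an amendment and one short item, asked twice per visit, with no extra visit or staff. A visit 3 PSS taken before session 3 cannot reflect that session; only the momentary item can. Rewording would lose direct comparison with the norm table and make the recall length vary between women. Forms already collected need separate handling.
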